8 STUDY TREATMENTS

8.1 INVESTIGATIONAL MEDICINAL PRODUCT(S)

Olipudase alfa is a sterile, non-pyrogenic white to off-white lyophilized cake supplied in single-use, 20 cc Type 1 glass vials. Each vial contains 20 mg of extractable olipudase alfa.

The lyophilized powder will be reconstituted with 5.1 mL of sterile water for injection to yield a concentration of 4.0 mg/mL olipudase alfa, which will be further diluted in 0.9% sodium chloride solution to a specific volume based on the dose to be administered.

Detailed instructions on the preparation, storage, and administration for study drug will be provided in the pharmacy manual.

See [Section 8.7](#) for product handling and complaints reporting.

8.1.1 Treatments administered

The term “study drug” will refer to olipudase alfa and placebo (saline [0.9% sodium chloride solution]), but only olipudase alfa is an IMP.

During clinical development of olipudase alfa, incremental changes were made to the olipudase alfa manufacturing process. The different processes are referred to as Process B, C(■) and C(■).

Dosing with study drug will be by intravenous infusion every 2 weeks (± 3 days) in reference to the date of the first infusion (Day 1) for each patient. The 52-week treatment period of the PAP will begin on Day 1 with the first infusion of study drug.

To maintain the double-blind, all patients regardless of treatment assignment will undergo dose escalation under the same conditions and according to the schedule provided in [Table 1](#).

All infusions will take place in a monitored setting with ready access to emergency resuscitation equipment and medications (see [Section 10.1](#) for information on timing for in-patient hospitalization). One rechallenge each will be allowed for doses administered at Week 0 (0.1 mg/kg olipudase alfa or placebo) and at Week 4 (0.3 mg/kg olipudase alfa or placebo). Patients who are unable to tolerate the rechallenge at those doses will be discontinued from the study. If a patient is discontinued due to inability to tolerate rechallenge, (ie, a second dose of 0.3 mg/kg olipudase alfa), then an additional patient may be randomized but only during the PAP. During the PAP and ETP, in-patient hospitalization will be required preinfusion and for at least 24 hours after the infusion during dose escalation (ie, through Week 16 and Week 70, respectively) and may be required at the quarterly and yearly visits up through the end of Year 2; in-patient hospitalization may be necessary during quarterly and yearly study visits in Years 3 through 5.

Home infusion may be initiated during COVID-19 (ETP) by trained home nurses every 2 weeks (± 3 days), if agreed between the investigator and the sponsor, in compliance with applicable country-specific regulations. Patients must meet specific eligibility requirements ([Section 10.1.1](#)). Patients who initiated home infusion during the COVID-19 pandemic, and continue to be on home infusion, may continue receiving home infusion by trained home nurses in the ETP every 2 weeks (± 3 days) until the end of the ETP (refer to [Appendix B](#) for Germany).

For the switch from Process C(■) IMP to the updated manufacturing Process C(■) IMP, the patient should receive the first infusion at the site. However, If the site visit is not possible due to site closure or extenuating circumstances that prevent an in-person site visit (eg, during COVID-19 pandemic), the first infusion of Process C(■) is allowed during home infusion for eligible patients in agreement between the Sponsor and the Investigator, in compliance with applicable country-specific regulations.

For treatment periods during both the PAP and ETP, DLT criteria will apply. A rescue strategy will be implemented for patients who experience significant clinical decline (see [Section 8.1.6](#)).

Dose escalation will follow criteria described in [Section 8.1.3.3](#). Patients unable to tolerate the target randomized dose will receive the highest dose tolerable once every 2 weeks for the remainder of the study. The minimum active dose administered will be 0.3 mg/kg olipudase alfa.

8.1.2 Route and method of administration

Duration of study drug infusions will be the same regardless of treatment assignment and each infusion will last for approximately 220 minutes, except at W0 when it will last approximately 35 minutes and at W54 where it will last approximately 255 minutes.

For each patient, intravenous infusion with study drug should occur at approximately the same time of day. There are no restrictions on the infusion timing with respect to meals.

See [Section 8.1.3.2](#) for information on dose adjustments following dosing delays or missed infusions.

8.1.3 Dosing considerations

Dosing will be based on an individual patient's mass (ie, weight) as outlined in [Section 8.1.1](#). For patients with a body mass index (BMI) >30 , the dose will be based on the mass (in kilograms) corresponding to a BMI of 30 given the specific patient's height.

8.1.3.1 Dose adjustments

Dose adjustments may also be considered at any time in consultation with the sponsor and may be recommended based on current safety or efficacy analysis results obtained from completed or ongoing clinical studies with olipudase alfa.

8.1.3.2 Dosing delays or missed doses

Patients will be infused with study drug once every 2 weeks (± 3 days) with all infusions scheduled relative to the first study infusion on Day 1 of Week 0. If a study drug infusion is delayed by more than 3 days, then that infusion will be considered a missed infusion and will not be administered. The patient will receive the last previously tolerated dose of study drug upon return to the clinic for the next scheduled visit. During any dose escalation period, if more than 1 consecutive infusion is missed, then the next infusion will be reduced by 1 dose level.

Outside a dose escalation period, or if the patient has already reached his/her maximum tolerated dose, for a patient who has missed 2 consecutive doses:

- If the last dose was 0.3 mg/kg or 0.6 mg/kg, the patient should receive the same dose at the next scheduled infusion and for the rest of the study period.
- If the last dose was 1, 2, or 3 mg/kg, the first reintroduction dose should be 1 level below the last dose.
 - During this dose re-escalation, the schedule of assessments (except PK) will be similar to dose escalation period starting from the corresponding dose.
 - If this dose re-escalation happened during the PAP, re-escalation of 0.6 mg/kg will correspond to Week 6, repetition of 0.6 mg/kg will correspond to Week 8, 1 mg/kg to Week 10, 2 mg/kg to Week 12 and 3 mg/kg to Week 14 assessments.

Outside a dose escalation period, or if the patient has already reached his/her maximum tolerated dose, a patient who has missed 3 or more consecutive doses:

- If the last dose was 0.3 mg/kg, the patient will receive a dose of 0.3 mg/kg at the next scheduled infusion and for the rest of the study period.
- If the last dose was 0.6, 1, 2, or 3 mg/kg, the first reintroduction dose will be 0.3 mg/kg (0.3 mg/kg should be repeated at the subsequent infusion, similar to dose escalation schedule).
 - During this dose re-escalation, the schedule of assessments (except PK) will be similar to dose escalation period starting from the corresponding dose.
 - If this dose re-escalation happened during the PAP, re-escalation of 0.6 mg/kg will correspond to Week 6, repetition of 0.6 mg/kg will correspond to Week 8, 1 mg/kg to Week 10, 2 mg/kg to Week 12 and 3 mg/kg to Week 14 assessments.

Following this first reintroduction dose, the dose will be escalated at subsequent infusions up to the dose the patient had previously reached prior to the interruption (target dose or maximum tolerated dose) following the standard escalation process described in [Table 1](#).

Outside the dose escalation period during ETP, patients who require dose reintroduction will have the following assessments at each infusion until reaching their target or maximum tolerated dose of olipudase alfa:

- Continuous monitoring of AE/SAE and concomitant medications and therapies (see study manual).

- Abbreviated examination of general appearance before and after infusion
- Before infusion: vital sign measurements, liver function tests (LFTs), hematology tests and safety biomarkers and if available during home infusion from the same blood sample, clinical chemistry, multiplex assay and pharmacodynamic biomarkers.
- Immediately after infusion: vital sign measurements.
- 24 hours after infusion: vital sign measurements, LFTs, hematology and safety biomarkers and if available during home infusion from the same blood sample, clinical chemistry, multiplex assay and pharmacodynamic biomarkers.
- 48 hours after infusion: vital sign measurements, LFTs, hematology and safety biomarkers and if available during home infusion from the same blood sample, clinical chemistry, multiplex assay and pharmacodynamic biomarkers.
The 48 hours assessments after infusion will no longer be assessed after the cutoff date for a planned second database lock of the study for purpose of regulatory submissions in 2021.
- Urine β -HCG for pregnancy every 4 weeks as described in “footnote k” in [Section 1.2.2.1](#).

During the dose escalation period, for transaminases assessed after infusion, if any AST or ALT value is $> 2x$ baseline and $>ULN$, the test should be repeated prior to the next scheduled infusion. Depending on the test results, the dose can be adjusted (repeated or reduced) or treatment can be withheld to allow additional transaminase monitoring, based on the physician’s clinical judgment.

Baseline is defined as the following:

- For initial dose escalation: last values prior to first dose of olipudase alfa
- For dose re-escalation: last values prior to the first re-escalation dose

Dose reintroduction will be done at the site. During a regional or national emergency declared by a governmental agency such as the COVID-19 pandemic (refer to [Appendix B](#) for Germany) or extenuating circumstances that prevent an in-person site visit, dose reintroduction can take place via home visits in compliance with applicable country-specific regulations applying criteria in [Section 10.1.1](#) and performing the same dose reintroduction list of assessments (see study manual for details).

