In-patient hospitalization will be required before the start of the infusion and until at least 24 hours after the end of infusion during dose escalation (ie, through Week 16 [PAP]/Week 70 [ETP] if no dosing adjustments are necessary) and may be required during quarterly visits up through the end of Year 2; in-patient hospitalization may be necessary during quarterly and yearly study visits in Years 3 through 5. Blood will be collected and safety assessments performed 24 and 48 hours after the end of infusion. After the cut-off date for a planned second database lock of the study for purpose of regulatory submissions in 2021, the 48 hours post-infusion blood samplings will no longer be collected. For all other visits, patients will be observed after the end of infusion for at least 1 hour. Study drug infusions will occur once every 2 weeks (± 3 days) in

reference to the date of the first infusion (Day 1) for each patient, at the site or at home during a regional or national emergency declared by a governmental agency such as the COVID-19 pandemic (refer to [Appendix B](#) for Germany) if agreed between the investigator and the sponsor for eligible patients, in compliance with applicable country-specific regulations. Quarterly visits will occur at the site. If site visits are not possible and home infusion is already approved for the eligible patient, quarterly visits will be done at home. In such a case, some of the quarterly visit assessments can be done by the site through the phone (eg, [Health-related quality of life instruments](#)). The rest of the missed quarterly visit assessments will be done as unscheduled, as soon as site visits become available.

Telehealth visits are an acceptable alternative to site visits during the COVID-19 pandemic, in accordance with institutional policy and with applicable country-specific regulations. Patients who initiated home infusion during the COVID-19 pandemic, and continue to be on home infusion, may continue receiving home infusion by trained home nurses in the ETP every 2 weeks (± 3 days) until the end of the ETP (refer to [Appendix B](#) for Germany) and, in such case, telehealth visits may continue until the end of the ETP (except quarterly visits as specified above).

For the end of study/early discontinuation visit, assessments may vary depending on when discontinuation occurs.

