10.3.1 Temporary treatment discontinuation with investigational medicinal product(s)

Temporary treatment discontinuation corresponds to more than 1 dose not administered to the patient as decided by the investigator after consultation with the sponsor.

Temporary treatment discontinuation (also referred to as treatment interruption) may be considered by the investigator because of suspected AEs.

Re-initiation of study drug administration will be done under close and appropriate clinical/and or laboratory monitoring after the investigator has considered to his/her best medical judgment that the responsibility of study drug in the occurrence of the concerned event was unlikely and if the study selection criteria are still met ([Section 7.1](#) and [Section 7.2](#)). Before re-initiation of treatment, the sponsor must be consulted to determine the starting dose and if dose escalation will be required (see [Section 8.1.3](#)).

For all patients who have missed two or more doses that require reintroduction of olipudase alfa, the dose reintroduction will take place at the site. During the COVID-19 pandemic, if site visits are not possible and home infusion is already approved for the eligible patient, the investigator can decide whether reintroduction should occur at the hospital/study site or home visit.

Upon reintroduction of treatment, certain assessments will be repeated at infusions ([Section 8.1.3.2](#)). The investigator will decide if additional specific assessments may be required before the patient can begin the reintroduction regimen.

For all temporary treatment discontinuations, the duration will be recorded by the investigator in the appropriate screens of the eCRF.

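### The one-level-down rule for infusions missed during escalation has no tier for three or more, so a patient last at 1.0 or 2.0 mg/kg may restart at 0.6 or 1.0 mg/kg instead of 0.3 mg/kg

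*Protocol*

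**What the plan says.** Protocol 8.1.3.2 treats missed infusions differently by phase.

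- **During escalation.** After a single missed infusion the patient returns at the last tolerated dose. Beyond that there is one rule: "During any dose escalation period, if more than 1 consecutive infusion is missed, then the next infusion will be reduced by 1 dose level". It is the same for two missed infusions as for five.
- **Outside escalation, or at maximum tolerated dose.** There are two tiers. After two missed doses, a patient last at 0.3 or 0.6 mg/kg repeats that dose, and one last at 1, 2 or 3 mg/kg drops one level. The second tier, for longer runs, opens "Outside a dose escalation period, or if the patient has already reached his/her maximum tolerated dose, a patient who has missed 3 or more". Its restart dose is set further on: "If the last dose was 0.6, 1, 2, or 3 mg/kg, the first reintroduction dose will be 0.3 mg/kg". The 0.3 mg/kg dose is repeated and Table 1 is followed from there.

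Two other sections bear on this. Section 10.1 describes the escalation period as running "through Week 16 [PAP]/Week 70 [ETP] if no dosing adjustments are necessary". Section 10.3.1 says of temporary discontinuation: "Before re-initiation of treatment, the sponsor must be consulted to determine the starting dose and if dose escalation will be required". It refers back to 8.1.3 for the rules.

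On re-escalation after an interruption, 8.1.3.2 says "the schedule of assessments (except PK) will be similar to dose escalation period starting from the corresponding dose". The list for the extension period begins "Outside the dose escalation period during ETP, patients who require dose reintroduction will have the following assessments". The transaminase rule, which is written for the escalation period, gives this baseline: "For dose re-escalation: last values prior to the first re-escalation dose".

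**The concern.** A long gap lets substrate build up again, and the protocol treats that as the hazard. Section 4 attributes the toxicity seen in animals to the rate of substrate breakdown and expects gradual removal to lessen it. Section 9.7 says escalation exists to avoid a large ceramide release. Amended Protocol 12 (Appendix C) lowered the restart after three or more missed infusions from 0.6 to 0.3 mg/kg and gave safety as the reason. The escalation sentence has no matching tier.

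A patient in initial escalation has had less debulking than one who has finished it, yet on a literal reading can restart higher after the same gap. No section gives a reason for that. What is at stake is the safety of a single reintroduction dose, not any efficacy analysis.

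**Working it through.** The plan has no calculated figure to reproduce here. Its one stated number is the 0.3 mg/kg restart.

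**Inputs.** Dose ladder from Table 1 (8.1.3.3): 0.1, 0.3, 0.6, 1.0, 2.0, 3.0 mg/kg. Infusions are every 2 weeks. Escalation runs to Week 16 in the primary analysis period (PAP) and to Week 70 in the extension (6.1, 10.1). The PAP cutoff was 17 October 2019 (Appendix C, Amended Protocol 13), and SAP section 2 places it a few days after the last patient finishes PAP. The 0.3 mg/kg rule dates from Amended Protocol 12, 15 April 2020.

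**1. Length of the gap.** With k missed infusions the interval between doses is 2 × (k + 1) weeks. For k = 3 that is 8 weeks.

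**2. Restart dose after three or more missed.** The drop is read as one level below the last dose given, which fits the preceding sentence on the last tolerated dose.

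| Last dose (mg/kg) | Escalation rule | Three-or-more rule | Ratio |
|---|---|---|---|
| 0.6 | 0.3 | 0.3 | 0.3/0.3 = 1.0 |
| 1.0 | 0.6 | 0.3 | 0.6/0.3 = 2.0 |
| 2.0 | 1.0 | 0.3 | 1.0/0.3 = 3.3 |

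**3. Which rule applies on the nominal calendar.** For the extension crossover, add 54 to each week.

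| Last dose | Three missed | Missed by Week 16 | Return |
|---|---|---|---|
| Week 8 (0.6) | 10, 12, 14 | 3 | Week 16 |
| Week 10 (1.0) | 12, 14, 16 | 3 | Week 18 |
| Week 12 (2.0) | 14, 16, 18 | 2 | Week 20 |
| Week 14 (3.0) | 16, 18, 20 | 1 | Week 22 |
| Week 16 (3.0) | 18, 20, 22 | 0 | Week 24 |

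- If the missed visits decide, more than one falls inside escalation at 1.0 and 2.0 mg/kg, so the escalation rule applies and the 2.0- and 3.3-fold differences arise.
- If the return visit decides, returning by Week 16 requires a last dose by Week 16 − 8 = Week 8. The dose is then at most 0.6 mg/kg, where the escalation rule never gives more than 0.3 mg/kg. The difference disappears.
- If escalation counts as unfinished until the target is reached, the differences at 1.0 and 2.0 mg/kg arise whatever the calendar. The qualifier in 10.1 gives this reading some support.

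The protocol does not choose among these.

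**4. Reach.** From Week 52 to Week 70 is 18 weeks. 17 October 2019 + 18 weeks = 20 February 2020, which is 55 days before 15 April 2020. Since 55/14 = 3.9, a patient would have had to be at least four infusions behind (16 April 2020) for initial escalation to overlap the 0.3 mg/kg rule. The current protocol is dated 1 November 2022.

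**5. Time to regain 3.0 mg/kg by Table 1.**
- From 0.3: 0.3, 0.3, 0.6, 0.6, 1.0, 2.0, 3.0 is six intervals, 12 weeks.
- From 0.6 (repeated): four intervals, 8 weeks.
- From 1.0: two intervals, 4 weeks.

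A restart at 0.3 mg/kg therefore costs 12 − 8 = 4 or 12 − 4 = 8 extra weeks.

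**The case against.** **The text may already give the safe answer.** On the nominal calendar the affected patients return at Week 18 or 20, after escalation has ended, and could be given 0.3 mg/kg under the second tier. This stands, which is why the point is conditional. It does not settle the matter, because the escalation sentence speaks of infusions missed during escalation and names no deciding visit.

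**Other provisions stand between the rule and the patient.** The sponsor must be consulted on the starting dose (10.3.1) and may adjust doses at any time (8.1.3.1). Interruptions for a potential dose-limiting toxicity go to the DMC (8.1.4). Hospital observation and post-infusion liver tests accompany initial escalation. IXRS assigns vials by dose level (8.4) and has previously held missed-dose rules that the protocol omitted (Appendix C, Protocol Amendment 08). These reduce the risk. None replaces the stated rule: 10.3.1 points back to it, 8.1.3.1 is discretionary, and the IXRS content cannot be seen here.

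**A reader might infer that re-escalation is a further, live gap.** The documents do not support that. Section 8.1.3.2 lists extension-period reintroduction as outside escalation. The 0.3 mg/kg rule also covers anyone who has already reached the maximum tolerated dose, which a re-escalating patient may well have done. The transaminase baseline sets a laboratory reference and does not define the scope of the missed-dose rule. At worst two rules overlap.

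**A reader might also extend the conflict to 3.0 mg/kg**, where one level down is 2.0 mg/kg, or 2.0/0.3 = 6.7-fold. On the nominal schedule at most one of the three missed infusions then falls inside escalation, so the trigger is not met. That figure needs escalation to be extended past Week 16 or 70.

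**Conclusion.** The inconsistency is real but conditional and minor. After three or more missed infusions, a patient still escalating and last at 1.0 or 2.0 mg/kg restarts 2.0- or 3.3-fold above 0.3 mg/kg, provided that the missed visits decide or that escalation counts as unfinished on return. If the return visit on the nominal calendar decides, there may be no difference. The wording leaves this open.

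The conclusion assumes that one level down is measured from the last dose given, and that 17 October 2019 is close to the last patient's Week 52. On that date scheduled initial escalation was over by about 20 February 2020, so current reach is close to nil. Week 52 results are unaffected.

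The ratios should not be read as risks. The documents give no figure for how much substrate re-accumulates over 8 weeks, so no harm is quantified.

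**What to change.** In 8.1.3.2:

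- Limit the one-level-down escalation rule to exactly two missed infusions.
- For three or more missed during escalation, restart a patient last at 0.6 mg/kg or above at 0.3 mg/kg, repeat that dose, then follow Table 1. Patients in initial escalation last at 0.1 or 0.3 mg/kg keep the present rule.
- State that missed infusions are counted from the last dose given, even if the return visit falls after Week 16 or 70.
- State that the 0.3 mg/kg rule governs three or more missed during re-escalation, and that a re-escalating patient last at 0.3 mg/kg restarts at 0.3 mg/kg and resumes Table 1. Without that clause the escalation rule could send such a patient to 0.1 mg/kg, and the second tier read literally would hold the patient at 0.3 mg/kg for the rest of the study.
- Check that IXRS matches.

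The cost is protocol wording and an IXRS check. The downside is that the few affected patients take 4 or 8 weeks longer to return to 3.0 mg/kg, with the matching assessments. The sponsor already accepts a restart at 0.3 mg/kg outside escalation.

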8.1.3.3 Escalation schema

See [Table 1](#) and [Figure 1](#) for the dose escalation schedule and algorithm, respectively. During dose escalation (PAP and ETP), patients will be admitted to the hospital as described in [Section 10.1](#).

Table 1 - Dose escalation scheme during the PAP

Study week PAP ^a	Scheduled study drug ^b dose	
Week 0 ^c	0.1 mg/kg	
Week 2	0.3 mg/kg	
Week 4 ^c	0.3 mg/kg	
Week 6	0.6 mg/kg	
Week 8	0.6 mg/kg	
Week 10	1.0 mg/kg	
Week 12	2.0 mg/kg	
Week 14	3.0 mg/kg	
Week 16	3.0 mg/kg	End of the mock dose escalation for patients assigned to placebo; end of true dose escalation for patients assigned to target dose 3.0 mg/kg.

a Study weeks do not account for rechallenges.

b Study drug means olipudase alfa and placebo.

c A rechallenge will be permitted only once at Week 0 and at Week 4.

[figure not shown]
The same dose-escalation schedule and conditions will apply for patients who cross over from the placebo arm during the PAP to the active treatment arm in the ETP, except that patients unable to tolerate the 1 rechallenge each allowed for doses administered at Week 54 (0.1 mg/kg olipudase alfa) and Week 58 (0.3 mg/kg olipudase alfa) will discontinue from the study and will not be replaced.

The following criteria will determine the next dose of study drug to be administered, provided the patient does not experience an AE that meets the DLT ([Section 8.1.4](#)). Only AEs not related to the patient's underlying condition will affect dose escalation. These criteria apply to AEs considered related to study treatment:

1. If the patient experiences no AE or a mild AE, escalate to the next dose.
2. If the patient experiences a moderate AE, repeat the same dose.
3. If the patient experiences a severe AE, decrease to the prior dose.

If a patient presents on the day of infusion either with an unresolved AE or an acute illness, neither of which meets the patient DLT criteria ([Section 8.1.4](#)), then study drug infusion may be withheld or administered at the discretion of the investigator. If it is not possible to administer a regularly scheduled infusion within the 3-day window allowed per protocol, see [Section 8.1.3.2](#).

Figure 1 - Dose escalation algorithm

